Trial Name:

Community-based transcranial direct current stimulation treatment for bipolar depression

Document date:

17/07/2023

Principal Investigator	[name][name], University of East London, [name]
Protocol contributors	[name], Centre for Affective Disorders, Institute of Psychiatry, Psychology and Neuroscience, King's College London [name], Technische Universität Dresden, Germany [name], Technische Universität Dresden, Germany [name], University College London
Clinicaltrials.gov ID	NCT05436613
Funders	Milken Institute (financial support) Flow Neuroscience (provision of Flow tDCS device)

Contents

TRIAL SUMMARY	2
1 RATIONALE	5
2 OBJECTIVES AND OUTCOME MEASURES/ENDPOINTS	5
3 TRIAL DESIGN	7
4 TRIAL SETTING	7
5 PARTICIPANT ELIGIBILITY CRITERIA	7
6 TRIAL PROCEDURES	8
7 TRIAL TREATMENTS	10
8 RECORDING AND REPORTING OF ADVERSE EVENTS	11
9 STATISTICAL ANALYSIS PLAN	14
10 REFERENCES	17
11 SCHEDULE OF EVENTS	18

TRIAL SUMMARY

Trial Title:	Community-based transcranial direct current stimulation treatment for bipolar depression	
Short Title:	Transcranial direct current stimulation therapy for bipolar depression (b-DEP)	
Trial Design:	Pilot, open-label, single arm design	
Trial Participants:	Participants will have a diagnosis of Bipolar disorder, in a current depressive episode of moderate severity, receiving pharmacological or psychological treatment, ages minimum 18 years, community-dwelling.	
Total number of participants planned:	50	
Treatment duration:	6 weeks	
Additional follow up duration:	3 months	
Total trial duration per participant:	5 months	
Estimated total trial duration:	1 year	
Planned trial sites:	Multi-site	
	Objectives	Outcome Measures
Primary Objective:	To assess the efficacy of tDCS treatment	clinical response as measured by MADRS score improvement of $\geq 50\%$ following the course of tDCS treatment
Secondary Objective:	To assess acceptability and safety of the intervention.	Participant retention at the end of the treatment who have completed a minimum of 15 tDCS sessions. Participant acceptability questionnaire scales tDCS Adverse Events Questionnaire at each session
Formulation, Dose, Route of Administration	Transcranial direct current stimulation (tDCS) device with a bifrontal montage at left dorsolateral prefrontal cortex (DLPFC) and cathode at right DLPFC (EEG positions F3 and F4, respectively). Stimulation is 2 mA, and electrode area is 35 cm ² . The intervention consists of a 6-week course of active tDCS, consisting of 5 sessions per week for the first 3 weeks followed by 2 sessions per week for 3 weeks, for a total of 21 tDCS sessions. The duration of each session is 30 minutes.	

ii. LIST OF ABBREVIATIONS

Define all unusual or 'technical' terms related to the trial. Add or delete as appropriate to your trial. Maintain alphabetical order for ease of reference.

AE	Adverse Event
AR	Adverse Reaction
CA	Competent Authority
CE	Conformité Européene (European Conformity)
CI	Chief Investigator
CRF	Case Report Form
CRO	Contract Research Organisation
CTA	Clinical Trial Authorisation
CTIMP	Clinical Trial of Investigational Medicinal Product
CTU	Clinical Trials Unit
DMC	Data Monitoring Committee
DSUR	Development Safety Update Report
EC	European Commission
EEG	electroencephalogram
EMEA	European Medicines Agency
EU	European Union
EUCTD	European Clinical Trials Directive
EudraCT	European Clinical Trials Database
EudraVIGILANCE	European database for Pharmacovigilance
GCP	Good Clinical Practice
GMP	Good Manufacturing Practice
GP	General Practitioner
HAMA	Hamilton Anxiety Scale
HRSD	Hamilton Rating Scale for Depression
IB	Investigator Brochure
ICF	Informed Consent Form
ICH	International Conference on Harmonisation of technical requirements for registration of pharmaceuticals for human use.
IMP	Investigational Medicinal Product
IMPD	Investigational Medicinal Product Dossier
ISF	Investigator Site File (This forms part of the TMF)
ISRCTN	International Standard Randomised Controlled Trials Number
MA	Marketing Authorisation
MADRS	Montgomery-Åsberg Depression Rating Scale
MHRA	Medicines and Healthcare products Regulatory Agency
MINI	Mini-International Neuropsychiatric Interview
MS	Member State
NHS R&D	National Health Service Research & Development
NIMP	Non-Investigational Medicinal Product
NIHR	National Institute for Health Research
PHQ-9	Patient Health Questionnaire
PI	Principal Investigator
PIC	Participant Identification Centre
PIS	Participant Information Sheet
Q-LES-Q	Quality of Life Enjoyment and Satisfaction Questionnaire
QA	Quality Assurance
QC	Quality Control
QP	Qualified Person
RCT	Randomised Control Trial
REC	Research Ethics Committee
SAE	Serious Adverse Event

SAR	Serious Adverse Reaction
SDS	Sheehan Disability Scale
SDV	Source Data Verification
SOP	Standard Operating Procedure
SmPC	Summary of Product Characteristics
SSI	Site Specific Information
SUSAR	Suspected Unexpected Serious Adverse Reaction
tbc	to be confirmed
tDCS	transcranial direct current stimulation
tDCS AEQ	tDCS Adverse Events Questionnaire
TMF	Trial Master File
TMG	Trial Management Group
TSC	Trial Steering Committee
UK	United Kingdom
YMRS	Young Mania Rating Scale

1 RATIONALE

While there has been some demonstrated efficacy for tDCS as a first-line treatment for depression, the studies to date have investigated tDCS that is provided in the clinic. This is a problem because the treatment requires daily clinic visits for several weeks which could limit its accessibility and uptake among patients. As tDCS is a portable and safe treatment, it could be provided at home.

The present study is a **proof-of-concept trial** to assess the efficacy, acceptability and safety of tDCS treatment for bipolar depression within a community-based setting.

The findings from the present study will be applied to the design of a multi-site, randomised sham-controlled trial of community-based tDCS treatment for bipolar depression.

The present study will also investigate EEG and neuropsychological correlates and potential predictors of clinical response.

1.1 Assessment and management of risk

Noninvasive transcranial direct current stimulation (tDCS) has been used in human for decades. These noninvasive current stimulation techniques use battery-powered current generator devices that have a built-in circuitry to limit the current above a certain level, typically 2 mA.

The most common **adverse events** are mild skin redness (54%) at the site of the electrodes, which resolves following stimulation, itching (39%) and tingling (22%), followed by headache (16%), discomfort (13%) and burning sensation (10%) (Brunoni et al., 2011, Sampaio-Junior et al., 2018). There is no significant difference in rates between active and sham tDCS, except for skin redness which is more common with active (54%) relative to sham tDCS (19%) (Sampaio-Junior et al., 2018). Participants have been unable to distinguish whether they were receiving active or sham tDCS though, and there have been no differences in the discontinuation rates for active and sham treatments, mean rates 10% and 12%, respectively (Meron et al., 2015). In our recent pilot study in unipolar depression, the discontinuation rate has been 7.6% (2 out of 26 enrolled participants).

The **risk of treatment-emergent mania or hypomania** is estimated to be around 4% with a course of active tDCS and 0.5% with sham tDCS, with no statistical difference between active and sham tDCS (Brunoni et al., 2017; Sampaio-Junior et al., 2018). While the rate is lower than the 5-9% risk associated with antidepressant medication, it might be higher than the risk of <1% associated with repetitive transcranial magnetic stimulation (Xia et al., 2008).

Protocols in human trials (≤ 40 min, ≤ 4 milliamperes, ≤ 7.2 Coulombs) have not produced any reports of serious adverse effect or irreversible injury with over 33,200 sessions and 1,000 participants with repeated sessions (Bikson et al., 2016).

2 OBJECTIVES AND OUTCOME MEASURES/ENDPOINTS

The aim of the present project is to investigate the efficacy, acceptability and safety of community-based tDCS treatment for bipolar depression

2.1 Primary objective

The primary objective is to assess efficacy as measured by clinical response following a course of tDCS treatment.

2.2 Secondary objectives

The secondary objectives are to assess the acceptability and safety of the tDCS sessions.

2.3 Outcome measures/endpoints

Clinical response as measured by clinician-rated MADRS score improvement of $\geq 50\%$ following the course of tDCS treatment.

2.4 Primary endpoint/outcome

Clinical response as measured by clinician-rated MADRS score improvement of $\geq 50\%$ following the course of tDCS treatment.

2.5 Secondary endpoints/outcomes

- 1) Participant retention at the end of the treatment who have completed a minimum of 15 tDCS sessions
- 2) Participant acceptability questionnaire scales
- 3) tDCS Adverse Events Questionnaire at each session (Brunoni et al., 2011)

2.6 Exploratory endpoints/outcomes

Exploratory measures:

- i. Trained rater measure of depressive symptoms: Montgomery–Åsberg Depression Rating Scale (MADRS) remission rate
- ii. Self-report measure of depressive symptoms: Patient Health Questionnaire (PHQ-9)
- iii. Trained rater measure of anxiety symptoms: Hamilton Anxiety Scale (HAMA)
- iv. Trained rater measure of manic symptoms: Young Mania Rating Scale (YMRS)
- v. Self-report measure of disability and impairment: Sheehan Disability Scale (SDS)
- vi. Self-report Quality of Life Enjoyment and Satisfaction Questionnaire (Q-LES-Q)
- vii. Self-report acceptability of tDCS from healthy controls.
- viii. EEG recordings will be acquired during an eyes-closed resting state for 10 minutes and eyes open resting state for 10 minutes using a mobile EEG device in participants' homes (Muse EEG; <https://choosemuse.com/>) (Hashemi et al., 2016). Resting state EEG will be acquired at baseline for healthy controls and at 2 timepoints for participants with bipolar depression: 1) at baseline, and 2) at the end of the 6-week course of treatment. EEG coherence, a measure of neural connectivity, will be examined as a potential surrogate outcome measure (Minuissi et al., 2012).
- ix. Neuropsychological measures: verbal learning (Rey Auditory Verbal Learning Test (RAVLT)) and information processing speed (Symbol-Digit Modalities Test (SDMT)) will be assessed in participants' homes. Neuropsychological assessments will be delivered to participants and administered by a research team member via video call. Our pilot data indicates feasibility and acceptance of the neuropsychological assessments as all participants had completed the assessments (26 out of 26 participants). The measures will be acquired at baseline for healthy controls, and at 2 timepoints for participants with bipolar depression: 1) at baseline, and 2) at the end of the 6-week course of treatment.

Exploratory outcomes:

- 1) MADRS score ≤ 9 following the course of tDCS
- 2) Improvement in self-reported depressive symptoms as measured by PHQ-9
- 3) Improvement in anxiety symptoms as measured by HAMA
- 4) No significant increase in manic symptoms as measured by YMRS score >13
- 5) Improvement in disability experience as measured by SDS
- 6) Improvement in quality of life as measured by Q-LES-Q
- 7) Healthy control participant baseline acceptability questionnaire.
- 8) We hypothesize that increased functional connectivity in the resting state default mode network is linked with an improvement in depressive symptoms at the end of treatment.
- 9) We will apply machine learning analysis to examine the potential of resting state EEG coherence to predict clinical response (Al-Kaysi et al., 2016).
- 10) Effects on cognitive functioning as measured by neuropsychological tasks.

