5.1.2 Exclusion criteria

- any concurrent psychiatric disorder, including obsessive compulsive disorder
- having a significant risk of suicide
- score greater than 8 in the Young Mania Rating Scale
- exclusion criteria for tDCS, including having a scalp or skin condition (e.g. psoriasis or eczema); if contact with the scalp is not possible; having metallic implants, including intracranial electrodes, surgical clips, shrapnel or a pacemaker

- history of epilepsy
- history of a seizure which resulted in a loss of consciousness
- neurological disorder or history of migraines

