9 STATISTICAL ANALYSIS PLAN

9.1 Sample size calculation

Based on an effect size of $d = 0.70$ (Meron et al., 2015; Mutz et al., 2018) following a 6-week course of tDCS treatment (consisting of 15-21 sessions) with 90% power, we will enrol 50 participants to achieve a sample size of 45 participants with bipolar depression who will complete the course of treatment, based on a 10% attrition rate.

[figure not shown]

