9.3.3 Secondary outcome analysis

The secondary outcome analyses are; participant retention, which will be measured by the number of enrolled participants who do not drop out before the 6 week course of tDCS, divided by the total number of enrolled participants, expressed as a percentage; Acceptability, which will be measured by the percentage of participants rating the intervention as acceptable at the end of the 6 week course of tDCS. The acceptability scale consists of the question 'How acceptable did you find the tDCS

sessions?' with responses ranging from 'Very unacceptable' to 'Very acceptable' on a 7-point anchored Likert scale with the acceptable ratings being from rating 5-7, and safety outcomes, which will be measured by calculating the number of severe, moderate and mild adverse events and their relation to the intervention.

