9.8 Procedure(s) to account for missing or spurious data

Any missing data will be imputed in a last observation carried forward model.

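### The one outcome aimed at manic switch (exploratory outcome 4) is ambiguously worded, has no stated analysis and is subject to LOCF; a count with an exact confidence interval should replace it

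*Combined protocol and SAP*

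**What the plan says.** Section 1.1 treats mania or hypomania as a risk in its own right. It "is estimated to be around 4% with a course of active tDCS and 0.5% with sham tDCS", and the text then compares it with drug treatment: "While the rate is lower than the 5-9% risk associated with antidepressant medication".

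Safety is a secondary objective (Section 2.2). The secondary safety endpoint in Section 2.5 is the tDCS Adverse Events Questionnaire. Section 9.3.3 analyses safety by "calculating the number of severe, moderate and mild adverse events and their relation to the intervention". Neither place names manic switch.

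The YMRS appears as an outcome only in Section 2.6, among the exploratory outcomes: "No significant increase in manic symptoms as measured by YMRS score >13". Section 9 gives no YMRS analysis: no test, alpha, comparator, acceptable number of cases or interval.

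Three other provisions bear on this outcome:
- **Entry.** Section 5.1.2 excludes anyone with a "score greater than 8 in the Young Mania Rating Scale", so nobody should start above 13.
- **Timing.** Section 11 schedules the YMRS at baseline, once in mid-treatment, at the end of treatment and at the 3-month follow-up.
- **Missing data.** Section 9.8 states: "Any missing data will be imputed in a last observation carried forward model". It makes no exception for safety outcomes.

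**The concern.** The wording supports two different rules. In one, significant is statistical: a test is run and a non-significant result is the favourable finding. In the other, significant is clinical, and a score above 13 is itself the definition of a significant increase. The plan does not choose, so the choice could be made after the data are seen.

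A sample of 50 supports only a limited statement under either rule. The statement could nevertheless be carried forward as reassurance, because Section 1 says that the findings will be applied to the design of a sham-controlled trial.

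LOCF adds a bias in one direction. Mania can itself cause a participant to leave: Section 6.10 provides for withdrawal after serious adverse effects. Someone who leaves between ratings has no YMRS at the time of the event, and the carried-forward score comes from before it. That score is at most 8 if only the entry rating exists.

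**Working it through.** **Inputs from the documents**
- Bipolar participants: 50 enrolled, 45 expected to complete (Section 9.1).
- Switch rate: about 4% active and 0.5% sham; 5-9% is quoted for antidepressants (Section 1.1).
- Entry YMRS at most 8 (Section 5.1.2), so any later score above 13 is a new event.
- Single arm (Trial Summary), so an increase most naturally means a change from baseline.

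**Assumptions**
- Alpha 0.05, because the documents state none.
- Participants are independent, and each switch is seen as a score above 13.

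**The plan's own figure.** Section 9.1 says "we will enrol 50 participants to achieve a sample size of 45 participants with bipolar depression", and 45 / (1 − 0.10) = 50, which reproduces. That sample size rests on an effect size of 0.70 for efficacy. No size or precision is stated for manic switch.

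**Reading A: a significance test.** The plan names none, so an exact McNemar test is used as an illustration. With nobody above 13 at baseline, all discordant pairs point upwards, and k new cases give a two-sided p = 2 × 0.5^k.
- k = 5: 2 × 0.03125 = 0.0625, not significant. 5/50 = 10%, above the quoted 5-9%.
- k = 6: 2 × 0.015625 = 0.03125, significant. 6/50 = 12%.

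The chance of at least 6 cases in 50 is 1.4% at a true rate of 4% and 29% at 9%. With a one-sided test (at least 5 cases) it is 4.9% and 47%. These figures depend on the test chosen. Against a fixed rate of 0.5% (one-sided 0.05, at least 2 cases), power at 4% is 60%, so the result would be non-significant 40% of the time.

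**Reading B: a threshold, with any score above 13 counted as a case.**
- At a true 4%: P(no case) = 0.96^50 = 0.130, so P(at least one) = 87%.
- At a true 9%: P(no case) = 0.91^50 = 0.009, so P(at least one) = 99%.

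**What 50 participants can show under either reading (exact Clopper-Pearson 95% limits)**

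| Cases / N | Percentage | 95% limits |
|---|---|---|
| 0/50 | 0% | 0 to 7.1% |
| 1/50 | 2% | 0.1 to 10.6% |
| 2/50 | 4% | 0.5 to 13.7% |
| 5/50 | 10% | 3.3 to 21.8% |

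For no cases, the upper limit is 1 − 0.025^(1/50) = 7.1%. The expected number at 4% is 0.04 × 50 = 2. With two cases the interval reaches from the sham figure to well above the antidepressant range.

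**LOCF.** With about two cases expected, one participant who leaves because of mania before the next rating matters. Two true cases scored as one change 4% (0.5 to 13.7%) into 2% (0.1 to 10.6%). This example shows the sensitivity; the documents do not say how often it would happen.

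**The case against.** The strongest objection is that the threshold reading is at least as natural as the test reading. Entry excludes scores above 8, exploratory outcome 1 is also a cut-off (MADRS of 9 or less), and the primary and secondary analyses in Section 9.3 are percentages and counts with no hypothesis test. A reader might infer that the plan declares safety by default. The documents do not support this: as a threshold, the outcome would show at least one case 87% of the time at a true 4%. This part of the objection stands. So does its corollary, that any power figure belongs to the reviewer's chosen test and not to the plan.

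A reader might also infer that mania escapes safety reporting. It does not. The adverse event definition in Section 8.1 is broad enough to cover it, Section 8.9 records events for 3 months after the last session, Section 9.3.3 counts them, and Section 6.10 records reasons for withdrawal. A participant who leaves because of mania should therefore appear in the adverse event counts; LOCF hides that person only in the YMRS outcome. What remains is that those counts are by severity and relation, with no switch percentage, denominator or interval.

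Finally, this is an exploratory outcome in a proof-of-concept trial, and no stopping rule depends on it. No formal power is needed, and none is asked for here. The point concerns what may be concluded from the result.

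**Conclusion.** The point holds as a matter of unclear wording, missing analysis and one-directional handling of missing data, for a risk that the protocol itself singles out. It should be corrected, but it does not show that the plan certifies safety automatically or overlooks mania.

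The firm figures do not depend on how the outcome is read: no case in 50 leaves an upper 95% limit of 7.1%, two cases give 0.5 to 13.7%, and the chance of no case at a true 4% is 13%. They assume 50 independent treated participants and, for the 13%, that the Section 1.1 rate applies to scores above 13. The McNemar figures and the 60% power are illustrations under an assumed alpha and an assumed test. The direction of the LOCF bias is clear; its size is not known.

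**What to change.** In Section 2.6, replace the wording of outcome 4 with an estimate: the number and percentage of treated bipolar participants with YMRS above 13 at any post-baseline rating or a recorded mania or hypomania adverse event, with an exact 95% confidence interval and no significance test. Report it alongside the safety outcomes in Section 9.3.3. Formal promotion to a secondary outcome is optional.

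In Section 9.8, exempt this outcome from LOCF and count withdrawal because of mania as an event. Using all treated participants as the denominator would otherwise silently score unexplained dropouts as non-events. So state how many have no post-baseline YMRS, and give a sensitivity result among those rated. If, for illustration, 5 of 50 were unrated and 2 cases were seen, the main result would be 2/50 (4.0%, 0.5 to 13.7%) and the sensitivity result 2/45 (4.4%, 0.5 to 15.1%).

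The cost is mainly wording, since the YMRS and adverse events are already collected. The plan must also say which recorded adverse event terms count, because the MINI is scheduled only at screening. The downside is a less favourable safety statement: the upper limit stays near 7% even with no cases.

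### Exploratory outcome 9 predicts yes/no response from EEG coherence although the MADRS score itself is available; a baseline-adjusted score target would usually keep more information at almost no cost

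*Combined protocol and SAP*

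**What the plan says.** - **Target of the EEG prediction.** Section 2.6, exploratory outcome 9: "We will apply machine learning analysis to examine the potential of resting state EEG coherence to predict clinical response".
- **Aim in the rationale.** Section 1: "The present study will also investigate EEG and neuropsychological correlates and potential predictors of clinical response". This is the only place that links neuropsychological measures to prediction of response. Outcome 10 in section 2.6 reads "Effects on cognitive functioning as measured by neuropsychological tasks" and names no prediction target. Section 9.3 contains no predictor analysis of either kind.
- **Definition of the target.** Section 2.4: "Clinical response as measured by clinician-rated MADRS score improvement of" at least 50% after the course. Sections 2.3, 2.7 and 9.3.2 use the same cut.
- **A related EEG analysis.** Outcome 8 hypothesises that "increased functional connectivity in the resting state default mode network is linked with an improvement in depressive symptoms at the end of treatment". Improvement is not cut there.
- **Data available.** The schedule of events (section 11) lists the MADRS at screening, the first treatment visit, mid-course, the end of the course and follow-up. Baseline EEG is also collected.
- **Sample size.** Section 9.1: "we will enrol 50 participants to achieve a sample size of 45 participants with bipolar depression who will complete the course of treatment". The allowance is for one participant in ten to drop out. It does not address the predictor analysis. The documents give no expected response rate, predictor strength, significance level or power for that analysis.

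**The concern.** Cutting a score into two classes removes the distinctions within each class. At the lowest eligible MADRS of 18, an end score of 10 (8/18 = 44% improvement) and an end score of 18 (0%) get the same label. So do end scores of 9 (50%) and 0 (100%). A prediction model trained on the label cannot use those differences, while one trained on the score can.

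Section 1 says that the findings will feed the design of a randomised sham-controlled trial. With about 45 patients there is little information for finding a predictor. A weaker target makes it more likely that a real EEG predictor is missed or its strength poorly estimated. Validating the model well does not recover what the label has removed.

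**Working it through.** **Inputs.** From the documents: 45 completers of 50 enrolled (9.1), the 50% cut (2.4), and the minimum baseline MADRS of 18 (5.1.1). Assumed, because the documents give nothing: true correlation r between one predictor and MADRS improvement of 0.2 to 0.5, response rate p of 30% to 70%, and a two-sided 5% test.

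**1. The plan's own figure.** Section 9.1 uses d = 0.70 and 90% power. With two-sided 5% assumed, a two-group comparison needs 2 × (1.960 + 1.282)² / 0.70² = 42.9, so 43 per group (44 with the t distribution), close to 45. Then 45 / 0.9 = 50. A single-group test at the same d needs 22 to 24. Neither calculation concerns prediction, so the plan has no power figure to compare with what follows.

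**2. Information kept by the cut.** For a linear predictor and a normally distributed improvement, the cut multiplies the correlation by f = φ(z_p) / √(p(1−p)), and the share of information kept is f².
- p = 50%: f = 0.798, f² = 0.637. 45 patients count as 45 × 0.637 ≈ 29.
- p = 30% or 70%: f = 0.759, f² = 0.576. 45 patients count as 45 × 0.576 ≈ 26.

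The loss is therefore 36% to 42%.

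**3. One predictor, n = 45.** Approximation: power = Φ(atanh(ρ) × √(n − 3) − 1.96), with ρ = r for the score and ρ = r × f for the label. At r = 0.4 and p = 30%, the score gives Φ(0.4236 × 6.481 − 1.96) = 78%. The label gives ρ = 0.4 × 0.759 = 0.304 and power of 53%. Simulation (20,000 bivariate normal replicates per cell) agrees. Losses are computed before rounding; 70% response equals 30% by symmetry.

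| r | p | Power, score | Power, label | Loss (points) |
|---|---|---|---|---|
| 0.2 | 50% | 26.2% | 18.3% | 7.9 |
| 0.2 | 30% | 25.9% | 16.6% | 9.3 |
| 0.3 | 50% | 52.6% | 35.5% | 17.0 |
| 0.3 | 30% | 52.9% | 32.4% | 20.5 |
| 0.4 | 50% | 79.2% | 58.7% | 20.4 |
| 0.4 | 30% | 79.3% | 53.8% | 25.6 |
| 0.5 | 50% | 94.5% | 80.7% | 13.9 |
| 0.5 | 30% | 95.2% | 75.5% | 19.7 |

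The loss is about 8 to 26 points, or about 8 to 25 with all 50 enrolled. Widening the inputs to r = 0.2 to 0.6 and response of 20% to 77% gives about 5 to 32 points.

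**4. The proposed target modelled directly.** Step 3 has no baseline variable and a generic improvement score. A closer model uses the end score adjusted for V1, against a true 50% cut of percentage change. One version assumed whole-number scores, a baseline floor of 18, baseline mean 26 and SD 5, and a percentage-change SD of 30 points. It gave 49–50% against 33–36% at r = 0.3, and 75–77% against 53–59% at r = 0.4. Across the versions run, the loss was about 7 to 23 points.

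**5. Several features.** For a five-fold cross-validated ridge model with 10 equally weighted features (n = 45, response 30% or 50%, 1,000 replicates), power was 40–43% against 19–29% at a true R² of 0.2. At 0.3 it was 70–72% against 39–40%. This is nearer to machine learning, but the design is still assumed.

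**6. Where the loss disappears.** Suppose that patients fall into two groups, with mean improvement 70% or 20% and SD 15 points, and the predictor relates to group. Power on the score against the label is then 28% v 30%, 46% v 49% and 65% v 68% at latent correlations of 0.3, 0.4 and 0.5. Here the label does no worse.

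**The case against.** The choice of a class label is defensible. It matches the primary endpoint, so the model predicts what the trial reports. The title of the study cited for outcome 9, as listed in section 10, describes classification of EEG oscillations, so a label follows the cited approach and allows comparison with published classifiers. The outcome is exploratory, lies outside the sample-size calculation, and no decision rule depends on it. Outcome 8 already relates EEG connectivity to uncut improvement. If patients do divide into two distinct groups, step 6 shows that the label loses nothing.

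Most of this stands, and it limits the point to a low-severity one. It does not remove it. Outcome 8 concerns increased connectivity accompanying improvement; it does not supply a model that predicts the score from baseline EEG. Comparability with published classifiers is kept by a secondary display. The documents do not say that outcomes fall into two groups, and under a continuous, single-peaked improvement the score did better in every setting computed.

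A reader might infer that all the EEG and neuropsychological predictor analyses rest on responder status. The documents do not support that: only outcome 9 specifies such an analysis, it covers EEG alone, and neuropsychological prediction is an aim in section 1 with no analysis behind it.

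**Conclusion.** The point holds for exploratory outcome 9, as a cheap improvement of low severity. If the predictor relates roughly linearly to a continuous, single-peaked improvement, the yes/no target gives up about 36% to 42% of the information. For one predictor with n = 45, a two-sided 5% test, r of 0.2 to 0.5 and response of 30% to 70%, that corresponds to about 8 to 26 points of power, or about 7 to 23 when the adjusted end score is modelled directly. The loss would largely vanish with two distinct outcome groups.

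It is tempting to read these figures as the power that the planned analysis loses. The documents do not support that: they announce machine learning with no test, significance level, predictor strength or response rate. The figures illustrate lost information under stated assumptions. Nothing here bears on the primary endpoint.

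**What to change.** In section 2.6, outcome 9, name the end-of-course MADRS score (visit 21 in section 2.7), adjusted for the V1 MADRS, as the main target of the EEG prediction model. Apply the same target to any neuropsychological predictor analysis carried out under the section 1 aim. Keep classification of responder status as a secondary display. Leave the primary endpoint in 2.4 and 9.3.2 as it is. Settle this before the predictor analysis is run, so that the target is fixed in advance.

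The cost is one or two sentences and a change of model target, with no new data, visits or patients. The small downside is that the main result becomes a predicted score, so comparison with published classifiers comes from the secondary display.
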